7.7.2. Hypoglycemia

Analysis population(s): Safety analysis set

Analysis parameter(s): Hypoglycemia

Analysis method:

The number and proportion of subjects experiencing hypoglycemia (blood glucose decreased, hypoglycemic coma, hypoglycemic unconsciousness, hypoglycemic seizure, hypoglycemia) in the adverse event tabulation period, and the incidence per 1000 person-years, will be presented by treatment group. The number and proportion of subjects and the incidence per 1000 person-years will be presented by hypoglycemia category and treatment group. The number and proportion of subjects experiencing hypoglycemia will also be presented by treatment period and treatment group. For the attached hypoglycemia PT list, the number and proportion of subjects experiencing each event, as well as the incidence per 1000 person-years, will be presented by treatment group and by SOC and PT (blood glucose decreased, hypoglycemic coma, hypoglycemic unconsciousness, hypoglycemic seizure, hypoglycemia).

Hypoglycemia Categories

Severe hypoglycemia, documented symptomatic hypoglycemia, asymptomatic hypoglycemia, probable symptomatic hypoglycemia, relative hypoglycemia

Treatment Period Categories (in weeks)

< 13, \geq 13 and < 26, \geq 26 and < 52, \geq 52 and < 78, \geq 78

Listings

Analysis population(s): Safety Analysis Sets

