9.2.4.7 Hypoglycemia

The (sub) investigator will monitor the subject for hypoglycemia from the first day of the run-in period until Day 14 of the follow-up observation period based on Appendix 4, “Hypoglycemia Symptom Survey Form” and the blood glucose measurement results.

At each subject visit, the (sub) investigator will have the subject bring in the “Hypoglycemia Symptom Survey Form,” and will check its contents. If the (sub) investigator determines, on the basis of the “Hypoglycemia Symptom Survey Form” and the blood glucose measurement results, that the subject has developed hypoglycemia, the (sub) investigator will note this in the hypoglycemia space on the case report form. If the (sub) investigator determines that a symptom that is not judged to constitute hypoglycemia is an adverse event, the (sub) investigator will enter this information in the

adverse event section of the case report form.

The (sub) investigator will obtain the following information about events that have been judged to constitute hypoglycemia, and will record this information in the case report form in accordance with "9.2.4.8 Adverse Events." Furthermore, if the (sub) investigator determines that an event constitutes asymptomatic hypoglycemia, then the (sub) investigator will promptly check the subject's condition.

- (1) Hypoglycemia symptoms: Details of observed symptoms of hypoglycaemia.
 - (2) Hypoglycemia categories: Hypoglycemia will be classified based on the categories shown in Table 9.2 below.

Table 9.2: Hypoglycemia Categories

- (3) Severity
 - (4) Date and time of onset: The date and time when the hypoglycemia was noticed.
 - (5) Outcome, date of outcome, time of recovery
 - (6) Blood glucose level, date and time of blood glucose level measurement: The blood glucose level at the onset of hypoglycemia, and the date and time of the measurement.
 - (7) The cause of the hypoglycemia: The cause of the hypoglycemia will be determined based on the following criteria.
 - a) None
 - b) No diet or delay of diet
 - c) Performed intense exercise
 - d) Other
 - (8) Date and time of food eaten before the onset of hypoglycemia, date and time medicine was taken
 - (9) Action taken with respect to TA-7284
 - (10) Non-investigational product action(s) taken
 - (11) Causal relationship to TA-7284
 - (12) Seriousness

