- k) Serious adverse events will be investigated from informed consent acquisition up until Week 4 of the follow-up observation period. Other adverse events will be investigated from after the start of the administration of the treatment period investigational product up until Day 14 of the follow-up observation period.
- l) The instructions on blood glucose self-measurement (SMBG) and on completing the hypoglycemia symptoms survey form will be given on the first day of the run-in period. Blood glucose self-measurements will be performed whenever possible when the patient experiences symptoms of hypoglycemia.

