4.12. Adverse Drug Reaction

Adverse events for which it has been determined that there is a “reasonable possibility” of there being a causal relationship to the investigational product will be handled as adverse reactions.

4.13. Period of Assessment of the Incidence Per 1000 Person-Years of Each Safety Endpoint

1. Subjects for whom the date of the visit at Week 4 of the follow-up observation period can be obtained

Period of assessment of the incidence per 1000 person-years (in years) = (Day of the visit at Week 4 of the follow-up observation period – First day of the treatment period + 1)/365.25

2. Subjects for whom the date of the visit at Week 4 of the follow-up observation period can not be obtained

Period of assessment of the incidence per 1000 person-years (in years) = (Final assessment time point^{*1} – First day of the treatment period + 1)/365.25

^{*1}Final assessment time point

If the day of discontinuation can be obtained: Day of discontinuation

If the day of discontinuation cannot be obtained: Day of the final scheduled visit^{*2}

^{*2}Day of the final scheduled visit

The latest date will be used, regardless of the allowable time window

5. Analysis Sets

The analysis of efficacy is performed in the full analysis set (FAS). In addition, a secondary analysis of the primary endpoint will be performed in the per-protocol set (PPS), as well. Safety analysis is performed in the safety analysis set. The data sets analyzed are defined below. The study sponsor finalizes the details of how the subjects are handled by the time of the database lock.

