Treatment period discontinuation		The day of treatment period discontinuation	Within 7 days of the day of treatment period discontinuation
Week 4 of the follow-up observation period		Week 104 of the treatment period (or the day of treatment period discontinuation)	28 to 42 days after the last day of the treatment period

*1: The first day of the run-in period should be within 4 weeks of the first day of the screening period.

*2: The first day of the treatment period is the day of the initial prescription of the treatment period investigational product.

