6.4. Handling of Event Endpoint Data

The time to initial event onset (in days)^{*1} and the time to censoring (in days)^{*2} will be used for the event data described in 1 through 14 below.

*1 and *2 are defined in “4.10 Periods of Assessment of Efficacy Endpoint Events.”

1. Composite endpoint of end-stage renal disease (ESRD) onset, doubling of serum creatinine, renal death, and cardiovascular (CV) death
2. Composite endpoint of CV death and hospitalized congestive heart failure
3. Composite endpoint of CV death, non-fatal myocardial infarction, and non-fatal stroke
4. Hospitalized congestive heart failure
5. Composite renal endpoint of end-stage renal disease (ESRD), doubling of serum creatinine, and renal death

6. CV death
7. All-cause death
8. The CV composite endpoint of CV death, non-fatal myocardial infarction, non-fatal stroke, hospitalized congestive heart failure, and hospitalized unstable angina

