7.7. Safety Analysis

7.7.1. Adverse Events

- Reported adverse events will be reclassified using MedDRA version 20.1.
- Events newly occurring following the administration of the investigational product and events that have worsened compared to their status prior to treatment initiation will be tabulated as treatment-emergent adverse events (TEAEs).
- SOCs will be tabulated and displayed in the internationally recognized order, and PTs will be tabulated and displayed in descending order of the number of subjects with said events in the active drug group, in descending order of the number of subjects with said events in the placebo group,

and in PT code ascending order.

- When counting the number of subjects with a particular event by PT, if the same subject experienced a different PT adverse event, then this subject will be counted once for each PT. If the same subject experiences the same PT adverse event multiple times, then this subject will be counted only one time for this PT.
- When counting the number of subjects with a particular event by SOC, if the same subject experienced a different SOC adverse event, then this subject will be counted once for each SOC. If the same subject experiences the same SOC adverse event multiple times, then this subject will be counted only one time for this SOC.
- When tabulating events by severity (severe, moderate, mild), subjects will be counted as described below.
 - (1) If the same subject experiences adverse events at different levels of severity, then this subject will be counted once, at the highest level of severity.
 - (2) If the same subject experiences multiple adverse events at the same level of severity, then this subject will be counted once, at this level of severity.
 - (3) If the same subject experiences the same adverse event multiple times, this subject will be counted once at the highest level of severity.
- Calculation of the incidence per 1000 person-years

Safety Endpoints

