Adverse events, adverse reactions, serious adverse events, serious adverse reactions, adverse events leading to study treatment discontinuation, adverse reactions leading to study treatment discontinuation, adverse events leading to death, adverse reactions leading to death, hypoglycemia, severe hypoglycemia, documented symptomatic hypoglycemia, asymptomatic hypoglycemia, probable symptomatic hypoglycemia, relative hypoglycemia, the adverse events in the PT list for hypoglycemia in the attachment, lower limb amputation, volume depletion, fracture, osmotic diuresis, renal-related adverse events, diabetic ketoacidosis, acute pancreatitis, urinary tract infection, upper urinary tract infection, female mycotic genital infection, male mycotic genital infection, hypoglycemia, malignancy

N: Safety endpoint sample size

P: Sum total of the assessment period (in years) of the incidence per 1000 person-years for each subject in the safety analysis population

Incidence per 1000 person-years = $N/P \times 1000$ (1000 subject-years)

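### Hypoglycemia incidence: person-time runs 14 to 28 days past the end of non-serious event collection, and no summary table counts repeat episodes

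*SAP*

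**What the plan says.** SAP 7.7.2 presents hypoglycemia by treatment group as number and proportion of subjects plus an incidence, and repeats this by category: "The number and proportion of subjects and the incidence per 1000 person-years will be presented by hypoglycemia category and treatment group". Treatment intervals get subjects and proportions only.

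SAP 7.7.1 computes the incidence as N/P × 1000. N is described only as the sample size of the safety endpoint. The denominator is "P: Sum total of the assessment period (in years) of the incidence per 1000 person-years for each subject in the safety analysis population". For adverse event tables, the counting rule in the same section is: "If the same subject experiences the same PT adverse event multiple times, then this subject will be counted only one time for this PT".

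SAP 4.13 sets each subject's period. Where the Week 4 visit date is available: "Period of assessment of the incidence per 1000 person-years (in years) = (Day of the visit at Week 4 of the follow-up observation period", less the first treatment day, plus 1, divided by 365.25. Otherwise the period ends at discontinuation or, failing that, at the last scheduled visit. SAP Table 6.2 places the Week 4 visit "28 to 42 days after the last day of the treatment period".

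Collection stops earlier. Protocol 9.2.4.7 monitors hypoglycemia "from the first day of the run-in period until Day 14 of the follow-up observation period". Note k to SAP 2.4.1 ends other non-serious adverse events at the same day and treats serious ones differently: "Serious adverse events will be investigated from informed consent acquisition up until Week 4 of the follow-up observation period".

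Protocol 9.2.4.7 also has the date and time of onset recorded for each event judged to be hypoglycemia.

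**The concern.** A rate needs its numerator and denominator to cover the same time. Here the denominator continues after collection of non-serious events has ended, so the stated rule gives a figure that is slightly too low. The same P is used for the other non-serious adverse event incidences listed in SAP 7.7.1.

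Hypoglycemia can also recur, it is a named safety endpoint, and Protocol 8.5.2.3 lets other diabetes drugs be added or changed. If N counts subjects, no summary table separates an arm with single episodes from one with the same number of affected subjects and many repeats. The reader would have to reconstruct this from the listings.

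**Working it through.** The documents give no expected hypoglycemia rate, so there is no planned figure to reproduce. The checks apply the SAP's own formula.

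**1. Window overrun (from the documents).** Take the first treatment day as day 0 and L as the last treatment-period day. Under SAP 4.13, P = L + 28 + 1 to L + 42 + 1 days. The non-serious collection window is W = L + 14 + 1 days. The incidence is understated by 1 − W/P.

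| Subject with a Week 4 visit | W (days) | P (days) | Understatement |
|---|---|---|---|
| Completer, L = 728 | 743 | 757 to 771 | 14/757 = 1.85% to 28/771 = 3.63% |
| Leaves at Week 52, L = 364 | 379 | 393 to 407 | 14/393 = 3.56% to 28/407 = 6.88% |
| Leaves at Week 13, L = 91 | 106 | 120 to 134 | 14/120 = 11.67% to 28/134 = 20.90% |

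**2. Table level (assumption: a share d stops evenly over 104 weeks, mean stopping day 364).**
- All attend the Week 4 visit, d = 0.3: mean L = 0.7 × 728 + 0.3 × 364 = 618.8. The overrun is 14/647.8 = 2.16% to 28/661.8 = 4.23%.
- Stoppers have no visit, d = 0.3: (0.7 × 14)/(0.7 × 757 + 0.3 × 365) = 1.53%, to (0.7 × 28)/(0.7 × 771 + 0.3 × 365) = 3.02%.
- Over d = 0 to 0.3 the ranges are 1.9% to 4.2% and 1.5% to 3.6%.

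**3. Insensitivity to recurrence (N read as subjects).** Take 150 completers in an arm, 30 of them affected (assumption), with P = 757/365.25 = 2.0726 years and W = 743/365.25 = 2.0342 years each.
- Planned incidence: 1000 × 30/(150 × 2.0726) = 96.5, whatever the number of episodes.
- Episode rate at 1, 2 or 5 episodes per affected subject: 1000 × 30 × (1, 2, 5)/(150 × 2.0342) = 98.3, 196.6 or 491.6.
- With negative binomial counts of dispersion k (assumption), total episodes are 150 × ((1 − p)^(−k) − 1)/k. At p = 0.2 and k = 1, 2, 4 this gives 37.5, 42.2 and 54.1 episodes from the same 30 subjects.

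**4. Size of the labelling question (assumptions: constant hazard, all completers, Day 14 window).** The rate with person-time ended at first event is −ln(1 − p)/W. Subjects over the whole window is p/W.
- p = 0.05: 25.2 against 24.6 per 1000 person-years, 2.5% lower.
- p = 0.10: 51.8 against 49.2, 5.1% lower.
- p = 0.20: 109.7 against 98.3, 10.4% lower.

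**The case against.** The strongest reply is that subjects over total follow-up is a defined, exposure-adjusted incidence, and that one common P for the whole SAP 7.7.1 list, including serious events and deaths, is a reasonable simplification. That stands for serious events, which are collected to Week 4. It does not cover non-serious events, but it explains why the effect is small.

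Protocol 13.3.3 asks only for numbers and proportions of subjects with hypoglycemia. The SAP delivers those and more, and the interval presentation and listings show some recurrence. So the episode table is an improvement; its absence breaches nothing.

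The term for the adverse event tabulation period is not defined in the visible SAP text, and the appendices are redacted. Even so, SAP 4.13 fixes P, and non-serious events after Day 14 are not collected.

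Three stronger readings may tempt a reader, and the documents do not support them.
- **That the planned figure is a biased first-event rate which would dilute a hazard ratio.** The SAP never calls it a first-event rate or a hazard, and plans no hypoglycemia hazard ratio or test. The loose wording of N even admits an episode count, for which person-time should not stop at first onset. What remains is a need to define N and label the rate.
- **That the SAP uses one incidence label with two denominators.** SAP 6.4 says that times to first onset and to censoring "will be used for the event data described in 1 through 14 below", but SAP 7.6.2.4 does not define the denominator of the efficacy incidence.
- **That the 953 adverse reactions in 474 of 1629 subjects in Protocol section 1 indicate recurrence.** They pool all types of reaction, so they say nothing about repeat hypoglycemia.

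**Conclusion.** The point holds as a minor one about descriptive safety reporting.

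The window mismatch follows from the documents alone. For a completer with a Week 4 visit, the incidence of non-serious events is understated by 1.85% to 3.63%. An early leaver who attends the visit contributes a larger proportional overrun. At table level it is roughly 1.5% to 4.2% under the assumed stopping patterns. It largely cancels between arms unless discontinuation or attendance at the Week 4 visit differs.

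The absence of any episode summary is the more useful thing to repair. It rests on reading N as subjects with at least one event. That is the sensible reading given the once-per-subject rule and the pairing with numbers of subjects, but the SAP does not state it. How much recurrence would go unseen cannot be sized from the documents, so the episode figures above are illustrations.

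Ending person-time at first event is a matter of labelling. It changes little when few subjects are affected, and about 10% if 20% are, assuming a constant hazard.

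**What to change.** In SAP 4.13 and 7.7.1:
- End person-time for the hypoglycemia and other non-serious adverse event incidences at follow-up Day 14, or at the last assessment if earlier, and count events in that same window.
- Keep Week 4 person-time for the serious-event incidences. Report any serious hypoglycemia between Day 14 and Week 4 there, and in a footnote to the hypoglycemia table, so that none is lost.
- State that N is the number of subjects with at least one event. Either label the rate as subjects per total follow-up time, or also give it with person-time ended at first event.

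In SAP 7.7.2, add one descriptive table of total episodes and episodes per person-year by treatment group and hypoglycemia category, with person-time to Day 14 and not cut at first event. Keep the subject-level tables.

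The cost is SAP wording and one table from data already in the case report form. There are two downsides. A few frequent reporters can dominate episode counts, which also depend on self-report because glucose is self-measured only when possible. And these incidences would use a different denominator from the serious-event tables, which a footnote should say.

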7.7.3. Adverse Events of Special Interest

Analysis population(s): Safety analysis set

Analysis parameter(s): Lower limb amputation, volume depletion, fracture, osmotic diuresis, renal-related adverse events, diabetic ketoacidosis, acute pancreatitis, urinary tract infection, upper

urinary tract infection, female mycotic genital infection, male mycotic genital infection, hypoglycemia, and malignancies

Analysis method:

For adverse events of special interest occurring in the adverse event tabulation period, the numbers and proportions of subjects experiencing said events, as well as the incidence per 1000 person-years, will be presented for each treatment group.

The number and proportion of subjects experiencing the event, as well as the incidence per 1000 person-years, will be presented by eGFR category ($\geq 30 \text{ mL/min/1.73 m}^2$ and $< 45 \text{ mL/min/1.73 m}^2$, $\geq 45 \text{ mL/min/1.73 m}^2$ and $< 60 \text{ mL/min/1.73 m}^2$, $\geq 60 \text{ mL/min/1.73 m}^2$ and $< 90 \text{ mL/min/1.73 m}^2$) and by treatment group.

In addition, for the events in the PT list of adverse events of special interest in the attachment, the numbers and proportions of subjects experiencing said events, and the incidences per 1000 person-years will be presented by treatment group and PT.

Listings

Analysis population(s): Safety Analysis Sets

7.7.4. Clinical Laboratory Tests

Analysis population(s): Safety analysis set

Analysis parameter(s): Hematology test parameters, blood biochemistry test parameters (except for the parameters for the efficacy assessments), urinalysis (quantitative) (except for the parameters for the efficacy assessments), urinalysis (qualitative), renal function biomarkers

Analysis method:

For the analysis parameters other than urinalysis (qualitative), descriptive statistics will be presented by treatment group for the values at each assessment time point and the changes therein. For the urinalysis (qualitative) parameters, the number and proportion of subjects at each assessment time point will be presented by treatment group and treatment category ((-), (+/-), (1+), (2+), (3+), (4+)). The number and proportion of subjects at each measurement time point will be presented for the change in treatment category compared to the first day of the treatment period, as well.

For analysis parameters other than urinalysis (qualitative) parameters, shift tables will be prepared by treatment group showing the treatment categories (low, normal, high) at the first day of the treatment period and at each assessment time point. For urinalysis (qualitative) parameters, shift tables will be prepared by treatment group showing the treatment categories (normal, abnormal) at the first day of the treatment period and at each assessment time point.

Listings

Analysis population(s): Safety Analysis Sets

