3.2 Inclusion Criteria

Patients will be eligible for enrollment in the study if all of the following criteria apply, and the patients are capable of providing consent. Furthermore, the clinical laboratory test values that have been centrally measured at a central laboratory will be used for the inclusion criteria assessments.

- (1) Japanese patients with age \geq 30 years at written informed consent acquisition.
- (2) Patients who have received diagnoses of type 2 diabetes based on the diagnosis criteria of the Japan Diabetes Society by the time of written informed consent acquisition.
- (3) Sex: Either
- (4) Inpatient/outpatient status: Outpatient
- (5) Patients who have been receiving dietary and exercise therapy for diabetes without any changes to the regimens since at least 12 weeks before the first day of the treatment period. However, this restriction will not apply if the exercise therapy cannot be continued because of a complication.
- (6) Patients who have been receiving angiotensin-converting enzyme inhibitor (ACE-I) or angiotensin II receptor blocker (ARB) drugs at the maximum approved dose since at least 5 weeks before the first day of the screening period (or at the maximum approved dose for hypertension if the drug has not been approved for an indication of diabetic nephropathy).

However, this restriction will not apply if the (sub) investigator determines that for medical reasons it would not be appropriate to use the maximum approved dose. Furthermore, the concomitant use of ACE-I and ARB drugs will not be permitted.

- (7) Patients with HbA1c $\geq 6.5\%$ and $\leq 12.0\%$ on the first day of the run-in period.
- (8) Patients with eGFR ≥ 30 mL/min/1.73 m² and < 90 mL/min/1.73 m² on the first day of the run-in period.
- (9) Patients with a median urine albumin/creatinine ratio (urine ACR) for 3 days' worth of first morning void urine collected within 1 week that includes the visit day on the first day of the screening period that is at least 300 mg/g Cr and not more than 5,000 mg/g Cr. Furthermore, if this criterion is not satisfied, the (sub) investigator may perform retesting during the screening period if he/she determines that it is medically appropriate. No rule is being established regarding the number of times retesting may be performed.

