3.3 Exclusion Criteria

Patients who meet any of the following exclusion criteria between the day of informed consent acquisition and the first day of the treatment period will be excluded from the study. Furthermore, clinical laboratory test values that have been assessed at a central laboratory will be used in the exclusion criteria assessments.

- (1) Patients with type 1 diabetes mellitus, diabetes mellitus resulting from pancreatic disorder, or secondary forms of diabetes (e.g., Cushing's syndrome, acromegaly).
- (2) Patients with genetic glucose/galactose absorption deficiencies or renal glycosuria.
- (3) Patients with conditions requiring strict blood glucose monitoring, such as patients with severe ketosis, diabetic coma or precoma, severe infection, or severe trauma, or pre- or post-operative patients; or patients with a history of diabetic ketoacidosis.
- (4) Patients undergoing dietary therapy that strictly restrict sugar intake.
- (5) Patients diagnosed with non-diabetic kidney disease.
- (6) Patients with a history of nephrectomy or renal transplant or patients who have received dialysis treatment.
- (7) Patients with resting systolic blood pressure ≥ 180 mmHg or resting diastolic blood pressure ≥ 100 mmHg measured by the study site on the first day of the run-in period or the first day of the treatment period.
- (8) Patients who are human immunodeficiency virus (HIV) antibody positive.
- (9) Patients with serious (e.g., requiring hospitalization for treatment or eligible for surgery) liver or kidney disease.
- (10) Patients with ALT $> 2 \times$ ULN or total bilirubin $> 1.5 \times$ ULN on the first day of the run-in period.
- (11) Patients with serum potassium > 5.5 mmol/L on the first day of the run-in period.
- (12) Patients with current or prior symptoms of Class IV cardiac failure according to the functional classifications of the New York Heart Association (NYHA).
- (13) Patients who develop myocardial infarction or cerebrovascular disorders in the 12 weeks before the first day of the treatment period. Patients who have undergone revascularization (e.g., stent placement or bypass surgery). Patients with concurrent unstable angina pectoris.
- (14) Patients with ECG findings requiring urgent diagnosis/assessment or intervention in the 12 weeks before the first day of the treatment period (e.g., newly emergent clinically significant arrhythmias or conduction disorders).

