9.2.4 Safety Assessment Parameters

9.2.4.1 Clinical Laboratory Tests

Blood samples will be collected at the following visits for the measurement of the following parameters at the central laboratory: the first day of the run-in period; the first day of the treatment period; and Weeks 4, 8, 12, 16, 20, 24, 28, 32, 36, 40, 44, 48, 52, 64, 76, 88, and 104 of the treatment period (or at treatment period discontinuation).

(1) Hematology test parameters

White blood cell count, red blood cell count, hemoglobin, hematocrit, platelet count, white blood cell differential (neutrophils, lymphocytes, monocytes, eosinophils, basophils)

(2) Blood biochemistry test parameters (except for the parameters for the efficacy assessments)

AST (GOT), ALT (GPT), ALP, LDH, gamma-GTP, total cholesterol, LDL-C, CPK, Na, K, Cl, Ca, inorganic phosphorus, Mg, HCO₃, ketone body differential (total ketone bodies, acetoacetic acid, 3-hydroxybutyric acid), total protein, urea nitrogen, serum creatinine, uric acid, total bilirubin, direct bilirubin, albumin

Urine samples will be collected at the following time points for the measurement of the following parameters: the first day of the treatment period, and Weeks 4, 8, 12, 24, 36, 52, 64, 76, 88, and 104 of the treatment period (or at treatment period discontinuation).

(3) Urinalysis (quantitative) (except for the parameters for the efficacy assessments)

Urine creatinine, urine Na,* urine K,* urine Cl,* urine Ca,* urine inorganic phosphorus,* urine Mg*

*: Creatinine adjusted value

Urine samples will be collected at the following study visits for the measurement of the following parameters: the first day of the treatment period, and Weeks 4, 8, 12, 16, 20, 24, 28, 32, 36, 40, 44, 48, 52, 64, 76, 88, and 104 of the treatment period (or at treatment period discontinuation).

(4) Urinalysis (qualitative)

Specific gravity, pH, urine protein, urine occult blood, urine ketones, urine bilirubin, urine urobilinogen, nitrite, white blood cell esterase

The blood and urine samples will be collected by the individual study sites, and will then be collected from the study sites by the central laboratory for measurement. The test result printouts provided by the central laboratory will be retained by the study sites.

The clinical laboratory test results will be considered abnormal values if they deviate from the central laboratory's reference values.

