7.1. General Methods

7.1.1. Calculated Descriptive Statistics

The types of descriptive statistics that will be calculated for each continuous data parameter are shown in Table 7-1.

Table 7-1. Types of Descriptive Statistics Calculated

Parameter	Calculated Descriptive Statistics
Descriptive Statistics	Numbers of subjects, mean values, SDs, medians, minimums, maximums

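### The low/normal/high laboratory shift tables cannot separate degrees of elevation, and no visible planned table counts subjects by size of elevation in each arm (minor point)

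*SAP*

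**What the plan says.** SAP 7.7.4 plans two summaries for every laboratory parameter except qualitative urinalysis. In the first, "descriptive statistics will be presented by treatment group for the values at each assessment time point and the changes therein"; SAP 7.1.1 lists the statistics as "Numbers of subjects, mean values, SDs, medians, minimums, maximums". In the second, "shift tables will be prepared by treatment group showing the treatment categories (low, normal, high) at the first day of the treatment period"; later visits are classed the same way. Listings are also planned.

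The categories rest on the reference range. Protocol 9.2.4.1 states: "The clinical laboratory test results will be considered abnormal values if they deviate from the central laboratory's reference values". The documents do not give the ranges.

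Protocol 3.3 sets the entry limits for three of these analytes. Criterion (10) excludes "Patients with ALT $> 2 \times$ ULN or total bilirubin $> 1.5 \times$ ULN on the first day of the run-in period", and criterion (11) excludes "Patients with serum potassium > 5.5 mmol/L on the first day of the run-in period". The rationale given there for these criteria is patient safety and ethics.

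**The concern.** A three-level table treats every value above the ULN alike. That has two consequences.

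- A subject who is already high on the first day of the treatment period has no higher category to move to. Any further rise is recorded as high to high.
- Among subjects who start normal, one who ends just above the ULN and one who ends at many times the ULN fall in the same normal-to-high cell.

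For ALT and bilirubin, entry above normal needs no assumption, because the limits are written as multiples of ULN. For potassium it depends on a ULN below 5.5 mmol/L.

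At stake is how sharply the between-arm laboratory comparison picks up marked elevations. Potassium deserves attention here: subjects have an eGFR of 30 to below 90 and take an ACE-I or ARB, at the maximum approved dose unless the investigator judges that medically inappropriate. The limits that the protocol treats as safety limits at entry appear in none of the safety tables described in the SAP text.

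**Working it through.** The plan states no figure to reproduce. The check has four steps.

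**1. What the shift table can distinguish.** With categories low, normal and high, and *high* meaning above ULN:

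| Start | Later value | Cell |
|---|---|---|
| ALT 1.8 x ULN (admitted) | 8 x ULN | high to high |
| ALT 1.8 x ULN (admitted) | 1.8 x ULN | high to high |
| ALT normal | 1.05 x ULN | normal to high |
| ALT normal | 10 x ULN | normal to high |

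The values are illustrative. The first pair share a cell, and so do the second pair. The entry limit applies on the first day of the run-in period, and the shift baseline is the first day of the treatment period about two weeks later. The first two rows therefore assume that the subject is still high at that visit.

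**2. What the descriptive statistics can distinguish.** If k of 150 subjects in an arm rise by 1.0 mmol/L in potassium and the rest do not change, the mean change is k x 1.0 / 150. That is 0.007 for k = 1, 0.020 for k = 3 and 0.033 for k = 5. The maximum shows that at least one subject had a large value at that visit, but not how many did.

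**3. Size, for potassium, under assumptions.** None of these inputs is in the documents: values normal with mean 4.5 and SD 0.4 mmol/L, ULN 5.0, and a treatment that raises potassium by 1.0 mmol/L in 5% of subjects.

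- Above 5.0 without effect: P(Z > 1.25) = 10.6%. With effect: 0.95 x 10.6% + 0.05 x P(Z > -1.25) = 0.95 x 10.6% + 0.05 x 89.4% = 14.5%. Ratio 1.4.
- Above 5.5 without effect: P(Z > 2.5) = 0.62%. With effect: 0.95 x 0.62% + 0.05 x 50% = 3.1%. Ratio 5, or about 1 against 5 subjects per 150.

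The same formulas over mean 4.4, 4.5 or 4.7, SD 0.4 or 0.5 and ULN 4.8 or 5.0 give a ratio of 1.06 to 1.58 for *high* and 1.55 to 7.7 for values above 5.5. Over that grid, 80% to 98% of *high* values without effect are at or below 5.5, that is, values the protocol accepts at entry. The absolute difference in the base case is larger for *high* (14.5 - 10.6 = 3.9 points) than above 5.5 (3.1 - 0.6 = 2.5 points), but it sits on a much larger background.

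**4. Whether creatinine belongs on the list.** In the SAP 4.8 formula, eGFR varies as creatinine to the power -1.094. With age held fixed, a 30% eGFR decline is creatinine x 0.7^(-1/1.094) = 1.385, and a 40% decline is x 0.6^(-1/1.094) = 1.595. A doubling is an eGFR change of 2^(-1.094) - 1 = -53.2%. Each of these is analysed by arm against the subject's own baseline, whatever the reference-range category (SAP 7.6.1, 7.6.2.1 and 7.6.2.4). SAP 7.6.2.3 also models eGFR change at each visit, and SAP 7.6.3.8 repeats the 30% and 40% declines and the eGFR model by run-in eGFR stratum. Creatinine is therefore not an example of the gap.

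**The case against.** The strongest reply is that the shift table is only one output. SAP 7.7.4 also gives statistics of the changes, with minimum and maximum, and listings. Protocol 9.2.4.8 makes a laboratory abnormality an adverse event if it is linked to a sign or symptom, if it is treated, if it leads to a change in the investigational product, or if the investigator otherwise finds it clinically significant. Only the last is open judgement. A worsening of an event counts as a new event, and assessment is double-blind. Protocol 13.3.3 asks for descriptive statistics for continuous data and shift tables for discrete data, so the numeric shift tables go beyond the protocol's commitment.

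Most of this stands. A reader might infer from the three-level categories that worsening from a high value cannot show at all. The documents do not support that: it holds for the shift table only. What remains is narrower. Means dilute a few large rises, the maximum is not a count, listings do not compare arms, and an adverse-event report requires one of those four conditions and is not a count at a fixed threshold.

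Three further limits apply. Urea nitrogen has no entry limit, so it cannot be cited as an analyte whose limit admits high values. The potassium ULN and scenario are assumed. The SAP appendices are redacted, so a list of thresholds there cannot be ruled out, although 7.7.4 refers to none.

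**Conclusion.** The point holds as a minor one. The planned shift tables cannot separate degrees of elevation, and the visible SAP text plans no count of subjects by size of elevation in each arm. For ALT and total bilirubin this follows directly from the documents. For potassium, the lack of separation above the ULN is certain, but entry above normal holds only if the ULN is below 5.5 mmol/L.

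The potassium figures illustrate that a higher cut-off responds more, in relative terms, to a few large rises. They do not show that the trial would miss a signal, and the documents do not support that reading. Nor do they support reading this as a gap in monitoring renal worsening in the lowest eGFR stratum, since the efficacy analyses and the eGFR-banded table of renal-related adverse events (SAP 7.7.3) cover that. Type I error, power, the primary endpoint and data collection are unaffected.

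**What to change.** In SAP 7.7.4, split the *high* category at limits the protocol already uses:

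- potassium above ULN: up to 5.5, and above 5.5 mmol/L;
- ALT above ULN: up to 2 x, and above 2 x ULN;
- total bilirubin above ULN: up to 1.5 x, and above 1.5 x ULN.

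Report the number and proportion of subjects by arm, and by the run-in eGFR band used elsewhere in the SAP (30 to <45, 45 to <60, 60 to <90). If the laboratory's potassium ULN is 5.5 mmol/L or higher, the potassium split does not apply. If the redacted appendices already hold such thresholds, a cross-reference in 7.7.4 is enough. No added categories are needed for creatinine or urea nitrogen.

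The cost is slightly longer tables with small counts in the top categories. No new data are needed. Fixing the cut-points before database lock avoids choosing them after the results are seen.
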